### 3.4 Concomitant Medications, Procedures and Nondrug Therapies

#### 3.4.1 Concomitant Medications

Concomitant medications are any prescription or over-the-counter preparations, including herbal products and “natural remedies,” used by a patient while participating in this clinical study.

For all concomitant medication use, an indication for its use should be provided. If the stated indication is a nonspecific condition (e.g., “rash”), documentation of the condition, as specific as possible, should be maintained in the patient’s clinical study records as source documentation.

Use of herbal medicine during the study is not prohibited but strongly discouraged. All herbal and natural remedies should be reviewed by the investigator and if considered safe, may be allowed to continue at the same dose.

To avoid confounding effects on study endpoints, changes in administration of chronic concomitant medications should be minimized and done only if deemed necessary by the PI.

##### 3.4.1.1 Phosphate Binders

When coadministered with roxadustat, in a clinical pharmacology study, the bioavailability of roxadustat was reduced. Patients should be advised to discuss with the Investigator when changing the dose or dosing time of their phosphate binder while taking study medication.

##### 3.4.1.2 Statins

When coadministered with roxadustat, in clinical pharmacological studies, hydroxymethylglutaryl coenzyme A reductase inhibitor (statin) exposure was increased 2- to 3-fold. Investigators should consider this interaction and local prescribing information when deciding on the appropriate statin dose for individual patients, bearing in mind the impact of ethnicity, other concomitant medications, renal and hepatic function. Goals of lipid lowering treatment should be maintained as clinically indicated. The dose of statins should not exceed the recommended daily dose in [Table 1](#).

**Table 1 Recommended Maximum Daily Dose of Statins**

Statins	Recommended maximum dose (mg/day)
Atorvastatin	40
Simvastatin	5
Rosuvastatin	5
Pravastatin	40
Fluvastatin	20
Pitavastatin	1
Lovastatin	20

#### 3.4.2 Supplemental Iron Use

Oral iron supplementation is allowed. IV iron use is prohibited, but may be considered if patient was iron-deficient and unresponsive to oral iron supplementation and lacking erythroid response to study medication. This would require discussion with the Medical Monitor.

### 3.4.3 Best Supportive Care

Best supportive care including RBC transfusion is permitted to ensure patient's safety. The PI and site staff will utilize their own institutional criteria for the determination of when to transfuse a patient. Use of any ESA (epoetin alfa, epoetin beta, darbepoetin or others) is not permitted (see [Appendix I](#)) and patients who receive an ESA will be discontinued from further treatment with study medication.

### 3.4.4 Emergency Procedure (Therapeutic Phlebotomy)

If there are clinical concerns for a patient's Hb levels being too high, the Investigator may decide to perform a therapeutic phlebotomy in addition to temporarily withholding the study drug. This should be documented and discussed with the Medical Monitor.

### 3.4.5 Prohibited Medications/Therapies/Substances

The following medications/therapies are prohibited from 8 weeks prior to screening through to the End of Treatment visit except for ESAs which are prohibited for 8 weeks prior to Week 1 Day 1 registration/randomization visit and at any time during the study (see first bullet below regarding ESAs)

- Any use of ESAs (erythropoietin stimulating agents) 8 weeks prior to Week 1 Day 1 registration/randomization, such as epoetin alfa, epoetin beta, darbepoetin, etc. (see [Appendix I](#)). Patients who receive an ESA during the study will be discontinued from further treatment with study medication. Patients who discontinue study medication early (for any reason) will remain in the study through the 52 week study period. Patients will have a 4 week follow-up visit after stopping study medication and then be followed up at a reduced visit schedule of every 8 weeks until the end of the study.
- Androgens
- IV iron (but oral iron is allowed)
- Agents intended to treat MDS, e.g., azacitidine, decitabine, thalidomide, or lenalidomide
- Granulocyte colony stimulating factors (G-CSF). Exception is that G-CSF can be used per package insert/local prescribing directions to treat infections and/or pancytopenia, but NOT as prophylaxis.
- Dapsone
- Acetaminophen >2 g/day for more than 7 days
- Investigational agents such as luspatercept, etc.

### 3.4.6 Contraception

Female patients of childbearing potential, if not practicing complete sexual abstinence, must agree to an acceptable method of contraception. Male patients (nonsurgically sterile; i.e., no vasectomy) with female partners of childbearing potential who are not on birth control must agree to use a barrier method of contraception (e.g., condom) or the female partner must agree to use contraception as described above unless practicing complete sexual abstinence.

Patients must agree to practice above contraceptive methods, as applicable, for the entire duration of the study, from registration/randomization through the EOT visit. It is highly recommended that they continue to practice the contraceptive methods for 12 weeks following

the last dose of study treatment. For patients discontinuing study medication prematurely, it is recommended that they continue to practice contraceptive methods for 12 weeks following the last dose of study treatment.

Pregnancy, spontaneous or therapeutic abortion, or events related to pregnancy must be reported ([Section 7.3.6](#)).

### **3.5 Safety Monitoring Plan**

Safety will be assessed throughout the study. A complete baseline profile of each patient will be established through demographics, medical history, clinical laboratory values, vital signs, physical examination (PE), and electrocardiogram (ECG). During the course of the study, vital signs and laboratory tests will be performed at regular intervals as described in schedule of assessments ([Appendix A](#) and [Appendix B](#)).

Blood pressure (BP) and heart rate (HR) should be assessed according to the guidelines described in [Appendix N](#).

A physical exam (PE) will be conducted during Screening, Day 1, Week 28, EOT and at the 4 Week post-EOT visit.

Any significant findings prior to administration of study drug will be considered as baseline conditions and will be captured as baseline medical history. Any clinically significant (CS) changes from baseline will be monitored throughout the study and appropriate interventions will be taken accordingly. Clinical laboratory tests may be assessed at additional times on unscheduled visits for safety reasons. Liver function abnormalities will be monitored according to drug-induced liver injury (DILI) guidance ([Appendix H](#)).

All adverse events (AEs), serious AEs (SAEs), and ongoing concomitant medication usage will be monitored and recorded throughout the study. SAE reports will be evaluated individually to assess the impact of the event, if any, on the overall safety of the product and on the study itself. Cumulative AEs will be monitored throughout the study. SAEs and AEs will be followed until resolved, deemed stable, or until the patient's 4-week post EOT visit. See [Section 7](#) for details on AE and SAE reporting.

### **3.6 Data Safety Monitoring Board**

A Data Safety Monitoring Board (DSMB) will be established prior to the start of the DB portion of the study and will oversee the study on a regular and pre-defined basis. The role and function of the DSMB will be defined in the DSMB charter. Of particular note, the likely initial starting roxadustat dose for the DB portion of the study is 2.0 mg/kg. This may be adjusted in agreement with the DSMB if supported by data review.

## 4 STUDY ENROLLMENT AND WITHDRAWAL

### 4.1 Inclusion Criteria

A patient is eligible for the study if all of the following criteria are met:

1. Diagnosis of primary MDS (confirmed by bone marrow aspirate and biopsy prior to treatment Day 1), classified by the IPSS-R as very low, low, or intermediate risk with <5% bone marrow blasts. There is no minimum time from diagnosis to registration/randomization except to allow for proper IPSS-R classification to be made, and to show transfusion dependence for patients in both portions of the study.
2. RBC transfusion requirement of either:
  - a. 2 to 4 pRBC over the 8-weeks prior to registration/randomization,  
OR
  - b. 1 pRBC during the 8-weeks prior to registration/randomization: Patients with 1 pRBC must have a documented history of requiring 1 pRBC/8-weeks in 2 consecutive periods of 8 weeks in the 16 weeks preceding registration/randomization
  - c. The PI and site staff will utilize their own institutional criteria for the determination of when to transfuse a patient.
  - d. **Open-Label patients only**, the requirement to demonstrate transfusion dependence can also be met by a PI starting this particular patient on pRBC transfusion during the screening period.
3. There is no restriction on prior use of recombinant erythropoietins or analogues (erythropoiesis-stimulating agents (ESAs)), except that the patient must not have received any ESA within the 8 weeks prior to Day 1 registration/randomization. ESAs include but are not limited to any recombinant human erythropoietin and other drugs listed in [Appendix I](#).
4. Hb  $\leq$ 10.0 g/dL during Screening period. Hb values are obtained at Screening Visit 1 and 2; only 1 value needs to meet the Hb  $\leq$  10.0 g/dL criteria. These values must be the Central Laboratory values. A third value may be obtained if necessary.
5. Age  $\geq$ 18 years
6. Body weight  $\geq$ 45 kg
7. ECOG performance status of 0, 1 or 2 at last screen visit (see [Appendix F](#))
8. Must be capable of giving written informed consent

### 4.2 Exclusion Criteria

Patients will be excluded if any of the following criteria are met:

1. Diagnosis of secondary MDS associated with prior chemotherapy, extensive radiation therapy (>25% of bone marrow reserve), and/or other significant chemical or radiation exposure
2. Previous diagnosis of IPSS-R high risk or very high risk MDS (see [Appendix G](#))

3. Planned myeloablative or craniospinal radiation during the study
4. Prior bone marrow or stem-cell transplantation (SCT)
5. Significant myelofibrosis (>2+ fibrosis)
6. MDS associated with 5q(del) cytogenetic abnormality
7. Screen serum erythropoietin level > 400 mIU/mL
8. Alanine aminotransferase (ALT) > 3 x ULN, **OR** aspartate aminotransferase (AST) > 3 x ULN **OR** TBili > 1.5 x ULN (see [Appendix H](#))
9. Azacitidine, decitabine, thalidomide, lenalidomide, G-CSF, or luspatercept, or any investigational drugs within 8-weeks prior to Day 1 treatment or plans to use any of these medications during the course of clinical trial participation
10. Anticipated use of dapsone at any dose amount or chronic use of acetaminophen or paracetamol >2.0 g/day during the study for more than 7 days
11. Clinically significant anemia, as determined by the investigator, due to non-MDS etiologies such as iron deficiency, vitamin B12 or folate deficiency, autoimmune or hereditary hemolysis or anemia or hemorrhage or hereditary anemia such as sickle cell anemia or thalassemia
12. Active infection(s) requiring systemic antibiotic therapy
13. Cockcroft-Gault calculated estimated glomerular filtration rate (eGFR) <30 mL/min
14. Thromboembolic event such as DVT, pulmonary embolism, myocardial infarction, stroke, or TIA, within previous 6 months
15. Current condition requiring anticoagulant, e.g., warfarin or enoxaparin, a factor Xa inhibitor such as rivaroxaban or apixaban, or a direct thrombin inhibitor such as dabigatran. Chronic use of low-dose aspirin is allowed.
16. Significant heart disease, including NYHA Class III or IV congestive heart failure, uncontrolled hypertension or hypotension, or significant valvular or endocardial disease that would put the patient at risk for thromboembolism
17. Clinically significant or uncontrolled ongoing inflammatory/autoimmune disease (e.g., rheumatoid arthritis, Crohn's disease, celiac disease, etc.)
18. History of significant liver disease or active liver disease
19. Major surgery planned during the treatment period
20. Known, active or chronic gastrointestinal bleeding
21. Known human immunodeficiency virus (HIV), hepatitis B or hepatitis C infection
22. Clinically significant or uncontrolled medical condition that would affect the patient's ability to participate in the study or confound the study's efficacy or safety results
23. History of leukemia or other active malignancy except localized and non-metastatic squamous or basal cell carcinoma of the skin, or cervical intraepithelial neoplasm; patients with a history of cured malignancy with no evidence of recurrence for at least 3 years are eligible

24. Previous recipient of roxadustat or another hypoxia-inducible factor prolyl hydroxylase inhibitor (HIF-PHI)
25. Pregnant or breastfeeding females

### 4.3 Treatment Discontinuation

Patients who discontinue study medication early (for any reason) will remain in the study through the 52 week study period. Patients will have a 4 week follow-up visit after stopping study medication and then be followed up at a reduced visit schedule of every 8 weeks until the end of the study.

Patients will be discontinued from treatment for the following reasons (below and [Appendix H](#) and [Appendix O](#)):

- a. Disease progression: Diagnosis of AML during the study
- b. Liver Function: Discontinuation of treatment will occur if:
  - ALT or AST  $>8 \times$  ULN
  - ALT or AST  $>5 \times$  ULN for more than 2 weeks
  - ALT or AST  $>3 \times$  ULN and TBL  $>2 \times$  ULN or international normalized ration (INR)  $>1.5$  (If INR testing is applicable/evaluated)
  - ALT or AST  $>3 \times$  ULN with the appearance of fatigue, nausea, vomiting, right upper quadrant pain or tenderness, fever, rash and/or eosinophilia ( $>5\%$ )

A patient who decides to discontinue treatment with study medication will always be asked about the reason(s) for discontinuation and the presence of AEs (if any). These data will be ascertained and documented by the investigator and recorded in the electronic case report forms (eCRF) as appropriate. The patient should return all study medications.

Reasons for permanent discontinuation of treatment with study medication:

- Patient's decision (subject no longer wants to continue study medication (i.e., withdrawal of consent)
- Investigator's decision that it is in the best interest of the patient to be withdrawn from the study
- AEs (including SAEs)
- Significant noncompliance with study procedures, as determined by Investigator or Sponsor
- Lack of efficacy
- Treatment with ESAs
- Patient is lost to follow-up
- Site terminated by the Sponsor
- Pregnancy
- Death

#### **4.4 Replacement of Patients**

Patients will not be replaced for this study.

#### **4.5 Study Termination**

This trial can be terminated by the Sponsor at any time for any reason.

#### **4.6 Blinding**

For the DB component of the study, the Investigator, study site staff, subject and the Sponsor and designees, are blinded to study drug assignment, but not to the dose. Additionally, all efforts should be made to keep subjects blinded to study Hb values.

##### **4.6.1 Maintenance of Blinding**

Neither the subjects nor the Investigators and their staff can distinguish the roxadustat tablets from the matching placebo tablets. Both will be identical in appearance, packaging, and labeling in order to maintain the blind.

##### **4.6.2 Planned and Unplanned Unblinding of Treatment Assignment**

Treatment assignments will be unblinded after the completion of the study.

Any intentional or unintentional breaking of the blind should be reported and documented. Breaking the blind (for a single subject) should be considered only when knowledge of the treatment assignment is deemed essential by the Investigator for the subject's care. Unplanned unblinding will result in the discontinuation of the subject's participation from the study. When possible and appropriate the blind will be maintained for Sponsor personnel responsible for analysis and interpretation of results at the study's conclusion.

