### **3.1.3 Follow-Up Period**

All patients who complete 52 weeks (of treatment with study medication) will undergo a 4 week follow-up period after the last dose of study medication.

Patients who discontinue study medication early (for any reason) will remain in the study through the entire 52 week study period. Patients will have a 4 week follow-up visit after stopping study medication and then be followed up at a reduced visit schedule of every 8 weeks after the final follow-up visit until the end of the study.

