12.3. Analysis of Double-Blind Efficacy Endpoints

12.3.1. Analysis of Primary Efficacy Endpoint

The primary efficacy endpoint for this study is proportion of patients who achieved TI ≥ 56 consecutive days (e.g., 8 weeks) since first dose in the first 28-week of treatment. TI is defined as the absence of any intravenous RBC transfusion (packed cell or whole blood) during any consecutive 56 days during the treatment period (e.g., Days 1 to 56, Days 2 to 57, Days 3 to 58). All RBC transfusions from 8 to 16 weeks prior to first dose until end of study will be recorded on CRF. TI will be estimated in the duration beginning with the first dose date (Day 1) and ending with the date of end of treatment or last visit date at

week 28, whichever comes earlier. RBC transfusions after end of treatment will be recorded on the CRF until the last visit at week 52 from first dose but will not be used to define TI.

The endpoint will be also analyzed for the end of the 52-week study treatment period as a secondary endpoint.

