12.3.3. Analysis of Secondary Efficacy Endpoints

All secondary endpoints measured for treatment periods will be analyzed both for the first 28 weeks of treatment and for 52-week study treatment period. Others will be analyzed for the time during the study. The secondary efficacy endpoints will be analyzed based on the FAS population unless it is specified otherwise. Analyses using the PPS will be used as sensitivity analyses.

12.3.3.1. Proportion of Patients who achieved TI ≥ 56 consecutive days anytime during the study

The proportion of patients who achieved TI for ≥ 56 consecutive days will be summarized using the FAS and PPS and will be compared between the two treatment groups. TI is defined as the absence of any intravenous RBC transfusion (packed cell or whole blood) during any consecutive 56 days anytime during the study. TI will be estimated in the duration beginning with the first dose date (Day 1) and ending with the end of study or treatment discontinuation due to AE/SAE or death, whichever comes earlier. RBC transfusions after end of treatment will be recorded on CRF until the last visit at week 52 from first dose and will be used to define TI.

The p-value obtained will be reported for the test of the null hypothesis that there is no difference between the two treatment groups.

Similar methods will be used as for the primary endpoint.

This analysis will take into account the potential intercurrent events as follows:

1. Treatment discontinuation due to any reasons: using Treatment-policy strategy: regardless of these intercurrent events occurred; the TI will be estimated using RBC transfusion records in the whole study duration.
2. Death: using Treatment-policy strategy: regardless of these intercurrent events occurred; Patients who died prior to week 8 will be classified as non-responders. TI will be estimated using RBC transfusion records for the study duration up to death.

12.3.3.2. Proportion of Patients Who Achieved $\geq 50\%$ Reduction in Number of pRBC Transfusions over 8 Weeks Compared to Their Baseline for Any 8 Week Period during the Study (Factor of Erythroid Response)

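### Protocol 4.6.2 ends study participation after unplanned unblinding, contradicting the rule that everyone who stops study medication is followed to Week 52

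*Protocol*

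**What the plan says.** **Unblinding.** Protocol 4.6.2 allows the blind to be broken for a single subject only when the investigator judges that knowing the assignment is essential to that subject's care. It then says: "Unplanned unblinding will result in the discontinuation of the subject's participation from the study". It mentions no later visit or data collection.

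**Stopping study medication.** Protocol 4.3 opens with: "Patients who discontinue study medication early (for any reason) will remain in the study through the 52 week study period". Section 3.1.3 says the same: "Patients who discontinue study medication early (for any reason) will remain in the study through the entire 52 week study period". The rule also appears in the Synopsis, in Protocol 3.4.5 and 6.3, and in SAP 3.1. Appendix B supplies the schedule: an end-of-treatment visit, a visit four weeks later, then visits every eight weeks to Week 52, with transfusions and adverse events recorded throughout.

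**Reasons for stopping.** The list of reasons in 4.3 describes the patient's own decision as "subject no longer wants to continue study medication (i.e., withdrawal of consent", and the investigator's as a "decision that it is in the best interest of the patient to be withdrawn from the study". Unblinding is not in the list.

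**Use of the data.** For Test 3 (transfusion independence of at least 56 days at any time during the study), SAP 12.3.3.1 says that "the TI will be estimated using RBC transfusion records in the whole study duration", and that transfusions after end of treatment are recorded "until the last visit at week 52 from first dose and will be used to define TI". Test 4 (SAP 12.3.3.2) and Test 7 (SAP 12.3.3.5) follow the same treatment-policy approach. For the primary endpoint, SAP 12.3.1 records post-treatment transfusions "but will not be used to define TI".

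**The concern.** A site that has broken the blind cannot obey both rules. One ends the patient's participation; the other keeps the patient in follow-up to Week 52. Sites may therefore act differently, and the patients concerned are not a random subset, because unblinding is reserved for cases where the patient's care depends on knowing the treatment.

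Three tests in the alpha-controlled sequence (SAP Table 4, Tests 3, 4 and 7) expect transfusion records after study medication stops. AML progression is a safety assessment over 52 weeks (Protocol 2.9, SAP 4.3). The adverse event reporting period runs to 28 days after the last study visit (Protocol 7.3.1), so ending participation early shortens it.

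**Working it through.** The point is a conflict of text, so most of the check is a comparison of passages.

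1. **Are the two rules about the same thing?** Section 4.6.2 ends participation in the study, not only study medication. Sections 3.1.3 and 4.3 keep the patient in the study after medication stops, for any reason. Neither cross-refers to the other. This is a direct contradiction.

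2. **Does it reach the primary endpoint?** No. SAP 12.3.1 closes the window at end of treatment or Week 28, whichever is earlier. For a patient whose medication has stopped, the primary outcome is the same whether or not follow-up continues.

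3. **Is power an issue?** No. The plan states at least 90% power for 160 patients at 3:2 (96:64), 35% versus 5%, two-sided Fisher's test at 0.05. Exact power is the sum over x and y of Bin(x; n1, p1) × Bin(y; n2, p2), taken over tables with Fisher p < 0.05. This gives 0.9988, so the stated figure is met. The re-estimated design (120 patients, 72:48, 56% versus 13%) gives 0.999. As a stress test only, suppose 20% of each arm left and counted as non-responders. The rates become 0.8 × 35% = 28% and 0.8 × 5% = 4%, and power at 96:64 is 0.9898. For the 140 enrolled, assumed to split 84:56, the rates become 0.8 × 56% = 44.8% and 0.8 × 13% = 10.4%, and power is 0.9963.

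4. **Does it reach Tests 3, 4 and 7?** Yes. Take 52 weeks as 364 days.
   - Test 7 needs 140 consecutive days. The latest qualifying run starts on Day 364 − 140 + 1 = 225. A patient removed before Day 140 cannot respond; the same patient kept in follow-up still could.
   - Test 3 needs 56 days. The latest start is Day 364 − 56 + 1 = 309. A patient removed before Day 56 cannot respond.
   - These are any-period endpoints, and SAP 5.4 makes no substitution for missing data unless the SAP specifies one. Early removal can therefore only lose a response, never add one. The effect on the treatment difference depends on which arm the unblinded patients are in.

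5. **Which of these patients lose nothing?** The derivation text in SAP 12.3.3.1, 12.3.3.2 and 12.3.3.5 also closes the window at treatment discontinuation due to an AE/SAE. Under that text, an unblinded patient who stops for an adverse event loses no analysed transfusion data through 4.6.2.

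6. **What safety information is lost?** Treatment-emergent events are counted only to 28 days after last dose (Protocol 8.3.6, SAP 14.1). Protocol 7.3.5.2 still asks for deaths and other SAEs after participation ends if they may reasonably be related to the study. What is lost is later AML, later deaths and SAEs judged unrelated, and scheduled laboratory follow-up.

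**The case against.** Several counter-arguments have force.

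- **A specific rule may override a general one.** Section 4.6.2 could be meant as a deliberate exception. Transfusion follows each site's own criteria (Protocol 3.4.3), so an investigator who knows the assignment may transfuse differently, and patient-reported outcomes may shift too. This trade-off is real. But the follow-up rule is stated without exception in both documents, and the possible bias is better met by flagging the data than by not collecting them.
- **The reason list in 4.3.** A reader might infer that equating a wish to stop medication with withdrawal of consent removes every voluntary stopper from follow-up. The documents do not support that. The phrase is one item in a list of reasons for stopping study medication, in a section that opens by keeping such patients in the study. It is ambiguous wording that invites miscoding, and the investigator-decision item has the same weakness.
- **Size.** A reader might assume that, say, 2 to 10% of the 140 enrolled are affected (0.02 × 140 = 2.8; 0.10 × 140 = 14) and read this as a shift of 2 to 10 percentage points. The rate has no source in the documents. The shift is an outer bound on an overall response rate, not on the treatment difference, and anyone who responded before leaving remains a responder.
- **Safety.** A reader might infer that all death and SAE follow-up is lost. The limits in step 6 of the working show that it is not.
- **Version.** The SAP is based on Amendment 03 (30 January 2020); the protocol available is Amendment 02. Test 3 is not among the secondary endpoints in Protocol 2.8.2. Whether 4.6.2 was changed cannot be checked.

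**Conclusion.** The contradiction between Protocol 4.6.2 and the follow-up rule stands. Applied literally, 4.6.2 truncates follow-up for a small, clinically selected group. This affects Tests 3, 4 and 7, apart from patients whose window already closes at AE/SAE discontinuation, and it affects later AML, death and unrelated SAE information. The primary endpoint and its power are not touched. No magnitude can be given, because the documents report no rate of unblinding. The wording in the 4.3 reason list is a secondary matter of clarity. The conclusion assumes that the quoted lines remain in force in Amendment 03.

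**What to change.** 1. Confirm whether these lines of 4.3 and 4.6.2 survive in Amendment 03.
2. Reword 4.6.2 so that unplanned unblinding does not by itself end data collection: visits, transfusion records and safety follow-up continue to Week 52 on the existing Section 4.3 and Appendix B schedule unless the patient withdraws consent to follow-up. How study drug is handled after unblinding is for the sponsor to reconcile and state; nothing is proposed here.
3. Record the date of unblinding and flag later data, so that transfusions and patient-reported outcomes collected with knowledge of treatment can be identified. Tests 3, 4 and 7 could then be repeated with the window closed at unblinding.
4. In the 4.3 reason list, separate stopping study medication from withdrawing consent to follow-up, and word the investigator-decision item as a treatment stop. Sites would then code these as SAP 6.2 tabulates them, with treatment and study discontinuation reported separately.

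The cost is a few sentences of protocol text, a data flag and a check that the CRF supports the distinction. No new visits are needed.
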